### **Severity**

Adverse events will be graded according to CTCAE v5.0.. For AEs not included in the protocol defined grading system, the following guidelines will be used to describe severity.

- Mild – Events require minimal or no treatment and do not interfere with the participant's daily activities.
- Moderate – Events result in a low level of inconvenience or concern with the therapeutic measures. Moderate events may cause some interference with functioning.
- Severe – Events interrupt a participant's usual daily activity and may require systemic drug therapy or other treatment. Severe events are usually potentially life-threatening or incapacitating.

### **Relationship to Investigational Product**

All AEs must have their relationship to study intervention assessed by the clinician who examines and evaluates the participant based on temporal relationship and his/her clinical judgment. The degree of certainty about causality will be graded using the categories below. In a clinical trial, the study product must always be suspect.

- Definitely Related – There is clear evidence to suggest a causal relationship, and other possible contributing factors can be ruled out. The clinical event, including an abnormal laboratory test result, occurs in a plausible time relationship to study intervention administration and cannot be explained by concurrent disease or other drugs or chemicals. The response to withdrawal of the study intervention (dechallenge) should be clinically plausible. The event must be pharmacologically or phenomenologically definitive, with use of a satisfactory rechallenge procedure if necessary.
- Probably Related – There is evidence to suggest a causal relationship, and the influence of other factors is unlikely. The clinical event, including an abnormal laboratory test result, occurs within a reasonable time after administration of the study intervention, is unlikely to be attributed to concurrent disease or other drugs or chemicals, and follows a clinically reasonable response on withdrawal (dechallenge). Rechallenge information is not required to fulfill this definition.
- Potentially Related – There is some evidence to suggest a causal relationship (e.g., the event occurred within a reasonable time after administration of the trial medication). However, other factors may have contributed to the event (e.g., the participant's clinical condition, other concomitant events). Although an AE may rate only as "possibly related" soon after discovery, it can be flagged as requiring more information and later be upgraded to "probably related" or "definitely related", as appropriate.

- Unlikely to be related – A clinical event, including an abnormal laboratory test result, whose temporal relationship to study intervention administration makes a causal relationship improbable (e.g., the event did not occur within a reasonable time after administration of the study intervention) and in which other drugs or chemicals or underlying disease provides plausible explanations (e.g., the participant's clinical condition, other concomitant treatments).
- Not Related – The AE is completely independent of study intervention administration, and/or evidence exists that the event is definitely related to another etiology. There must be an alternative, definitive etiology documented by the clinician.

### Expectedness

The Principal Investigator will be responsible for determining whether an AE is expected or unexpected. An AE will be considered unexpected if the nature, severity, or frequency of the event is not consistent with the risk information previously described for the study intervention.

#### 6.2.4 Pharmacokinetics (if applicable) – N/A

#### 6.2.5 Biomarkers (if applicable) – N/A

### 6.3 Study Procedures

6.3.1 **Study Schedule:** See figure 1. The study will consist of 5 visits: The enrollment visit, randomization, and 2 visits for clamp procedures following each diet and a virtual/telephone follow up visit.

Enrollment Visit 1	Screening and Consent. Discuss research procedures. Meet with a registered dietitian or trained research staff to discuss diet and education on keeping a diet record. Review of insulin pump and CGM data.
Randomization Visit 2 (Virtual/Telephone or in person)	Randomization will occur, as will discussion of subsequent diet (and how to obtain meals), study requirements, and next steps. Review of insulin pump and CGM data.
Clamp Visit 3	Hyperinsulinemic-euglycemic 2-step clamp followed by hypoglycemic clamp. Study questionnaires. Review insulin pump and CGM data. Discussion of washout period and next steps. Review of insulin pump and CGM data
Visit 4 (Virtual/Telephone or in person)	Discussion of subsequent diet (and how to obtain meals), study requirements, and next steps. Review of insulin pump and CGM data.
Clamp Visit 5	Hyperinsulinemic-euglycemic 2 step clamp followed by hypoglycemic clamp. Study questionnaires. Review of insulin pump and CGM data. Discussion of potential need for insulin dose changes and follow up.
Visit 6	Interviews will be conducted over the telephone or over zoom.

### 6.3.2 Informed Consent:

- Written informed consent will be obtained from legally authorized representatives for those under age 18 prior to conducting any study-related procedures.
- Written informed consent will be obtained from individuals at least 18 years of age.
- For those under age 18, written informed adolescent assent will be obtained from adolescents.
- Participants and legally authorized representatives will be given time to think about the study and ask questions as needed. We will discuss that non-participation in the study will not affect clinical care to minimize undue influence or coercion.

### 6.3.3 Screening

- Participants will be recruited from the Yale Pediatric Diabetes Center and Yale Diabetes Center clinics using flyers or by recommendation of their primary clinician. Participants will undergo pre-screening of their electronic medical record to evaluate study eligibility by review of medical history, as well as prior laboratory tests
- Participants will be recruited using social media (Facebook, Instagram, Twitter).
- Participants may reach out to the investigators after reading about the study on ClinicalTrials.gov.
- Participants who are not in the Yale Health System will be asked screening questions over the phone prior to the enrollment visit.
- If it has been longer than 2 months since the most recent HbA1c level, participants will be re-screened by obtaining a HbA1c at the pediatric diabetes research center.
  - **Request for waiver of HIPAA authorization for recruitment/screening purposes only**
  - We will need to review the potential subject's medical record prior to approaching them about the study in order to confirm that they are medically eligible. It is impractical to approach patients about the study if they are not medically eligible, given the time involved in approaching patients and the volume of patients seen at the various clinics. Once we have determined initial medical eligibility, we will then screen those patients in-person, or over the phone if patients have agreed to be contacted in this manner, to confirm all eligibility criteria has been met.
- **Recruitment Methods.** Potential subjects will be identified in several ways:
  1. At the time of routine, clinical visits with study investigators and their colleagues. They may be approached in-person about the study by clinical staff and/or research staff. This initial contact may be followed up with a phone call, email, letter or MyChart message if the patient is willing to speak to a research team member.
  2. Recruitment materials posted in the community and on social media (Twitter, Facebook, Instagram) via YCCI and/or study personnel accounts. The flyer may also be distributed to the YCCI "Help Us Discover" database of more than 12,000 individuals who have expressed interest in clinical research at Yale. Emails will be sent to this database periodically about the study. Information about the study will also be posted on the YCCI's website. In addition, the research team will enlist the help of the YCCI Cultural Ambassadors to advertise for the study at community organizations and events utilizing the recruitment flyer.
  3. Direct-to-patient recruitment via the Joint Data Analytics Team (JDAT). This is a behind-the-scenes electronic medical record search run by JDAT for the Yale New Haven Health System (YNHHS). This search will not identify potential participants to the researchers. Once JDAT identifies eligible patients, these

potential participants will be sent a message via MyChart. Potential subjects who do not use MyChart will receive a paper mailing. If no response is received, the YCCI Recruitment Center may follow-up with a phone call to determine interest. We will also utilize JDAT to generate weekly schedule reports of eligible patients being seen at Pedi and Adult Endo clinics.

- The following wording will be used in the email, letter or MyChart message patients receive via JDAT and otherwise describing the study and inviting them to participate:

“You are receiving this [email or message or letter] because you have type 1 diabetes and are at least 12 years old. You may be eligible to participate in a free and confidential research study investigating metabolic changes that occur on a high protein/low carbohydrate diet. This is an 8 week study with 6 study visits. In order to participate, you must:

- Be between the ages of 12 to <25 years old
- Have type 1 diabetes for at least 1 year
- Use an insulin pump for at least 2 months
- Have a HbA1c level < 10%
- Weigh at least 108 pounds
- Be willing to wear a continuous glucose monitor for the duration of the study
- Be willing to keep a daily diet record and follow dietary guidelines

During the study you will be provided with:

- 3 meals per day during the very low carbohydrate diet (2 weeks)
- Continuous glucose monitoring supplies for the duration of the study (if you do not already have one)
- Blood ketone meter and strips (you can keep these)
- Activity monitor and scale (you can keep these)
- Compensation is up to \$420

To learn more or to see if you are eligible to participate, click on “I am interested” or call the ‘Help us Discover’ recruitment call center at [name]. This message is automated and is sent in an electronic manner based on your health record; no one has been inside or viewed your medical chart. No action by you is required. You may ignore this message or click “not interested.” Thank you very much for considering being a part of research at Yale. To learn about future research opportunities, you may also create a volunteer profile through the Research Tab in MyChart. To opt-out of all future research communications, please call the ‘Help us Discover’ recruitment call center at [name] and select #3.”

#### 6.3.4 Enrollment

- Participants will be enrolled by research study staff identified in this protocol.
- After confirming that screening criteria have been met and informed consent has been obtained and documented, subjects will undergo a history and directed physical exam, anthropometric measures, and hemoglobin A1c. A HbA1c done in the past 2 months may be used.

#### 6.3.5 On Study Visits

##### Visit 1 (Screening/Enrollment):

- Screening for inclusion/exclusion criteria
- Written informed Consent/Accent completion prior to any study activities
- Participants will be asked permission to allow the serum and information collected during this research study to be used for future research purposes. The serum samples may be used by our research group to run additional assays related to the pathophysiology of diabetes.
- Demographic characteristics including education level, family income, number of individuals in the home
- Current diabetes care practices (frequency of self-monitored blood glucose (SMBG), insulin dosing, review of blood glucose values)
- Anthropomorphic measures (height, weight, BMI, vital signs)
- Physical exam, tanner staging
- Urine pregnancy test (if participant is post-menarche)
- Point of care HbA1c, obtained via fingerstick and measured by a Siemens DCA Vantage device, will be determined unless an A1c was measured in clinic within the past 30 days.
- Medical History: duration of diabetes, comorbidities, past medical history, social history, family history, medications, and allergies.
- Additional diabetes history including current/past use of CGM, insulin pump, and other modes of diabetes technology.
- A handout with 2 examples of the type of diet required will be provided to each participant at the time of or prior to consent.
- All participants will receive dietary instruction (by a registered dietitian or trained research staff) to review the dietary requirements. Each participant will be instructed on how to keep a food diary, estimate food portions and receive instructions on information required during dietary recall.
- Participants will meet with a diabetes care provider (i.e., a physician, nurse practitioner, or physician assistant) who will carry out a comprehensive review of diabetes management and review blood glucose and insulin dosing records. Insulin pumps and CGMs will be downloaded to assess glycemic control. The diabetes treatment regimen will be adjusted as clinically indicated.
- A CGM will be provided if the individual does not have one that they use as a part of routine care. Participants will be instructed on how to use these devices, as they would typically be instructed at clinic visits.
- CGM low alerts will be set at 55 mg/dL and 70 mg/dL. CGM high alerts will be individualized to each patient, but be kept consistent during both study dietary periods.
- Participants will receive an activity monitor (Fitbit or Garmin) if they do not already have one and instructed on its use. We will ask participants to maintain a consistent activity level throughout both dietary periods. You may keep the activity monitor (Fitbit or Garmin) that we provide for you.
- Participants will also receive a bioimpedance scale to use at home for anthropomorphic measurements.
- Participants will receive a blood ketone meter and ketone strips to use for the duration of the study.
- Questionnaires will be administered using Qualtrics or paper/pen, including:
  - Diabetes Treatment Satisfaction Questionnaire (DTSQ), which includes eight items, six of which form a scale (scored 0-36) in which higher scores indicate greater treatment satisfaction. (11)
  - Nutrition Knowledge Survey (NKS) which collects information on healthful eating, carbohydrate counting, blood glucose response to foods, and nutrition label reading. Higher NKS scores reflect greater nutrition knowledge (score range is 0-100%). (12)

- Clarke Hypoglycemia awareness questionnaire.
- Open-ended questionnaire regarding the diet (see Additional Documents)

**Follow Up Calls:**

- Participants will be followed up weekly to make insulin dose adjustments during the insulin optimization and washout periods. Insulin pump and CGM information will be reviewed during these phone calls.
- Participants will also be screened for any symptoms that may be related to very low carbohydrate diets on a weekly basis or more often as needed (symptoms including nausea, vomiting, abdominal pain, constipation, fatigue, and lightheadedness). If these occur, participants will be instructed to ensure adequate caloric intake is achieved and hydration is maintained.

**Visit 2 Randomization (virtual/telephone or in person):**

- Anthropomorphic measures (weight, % body fat, % muscle mass, % water, % bone) – home or on scale in office.
- Insulin pumps and CGMs will be downloaded to assess glycemic control. The diabetes treatment regimen will be adjusted as clinically indicated.
  - If participants are starting the very low carbohydrate diet, insulin doses will be reduced by 10-20%, as clinically indicated, to prevent hypoglycemia.
- First diet will be assigned.
  - If participants are starting the very low carbohydrate diet, meals can be picked up 2-3 times per week at the metabolic kitchen located at Yale New Haven Hospital by study participants or by research staff. Research staff will work with participants to deliver the meals if they are unable to pick them up.
  - If we are unable to acquire meals from the metabolic kitchen, we will use a mail order meal service that provides information about macronutrient content of all meals provided that meet the standards of the dietary measures.
- Participants will be instructed to check daily fasting blood ketone levels.
- Participants will receive dietary instruction and review the dietary requirements of the study. Participants will be instructed to keep a dietary record (MyFitnessPal application, written, and/or with photos) for the duration of the dietary period.
- Participants will be instructed to call the pediatric diabetes emergency line (available 24/7) in any case of severe low blood sugar, elevated ketone levels, or symptoms of ketosis. Participants will also receive education on the treatment of hypoglycemia, we will ensure that all participants have glucagon at home.
- Participants will be contacted 3 times per week (2 scheduled, 1 unscheduled) for a 24-hour dietary recall. During these telephone follow up calls, food diary will be reviewed, ketone levels reviewed, and CGM data will be uploaded and reviewed.
- Prior to the HRU/CSRU/Masonicare admission, we will recommend a standard diet be given and no food be eaten after 9pm (except for in cases of hypoglycemia). Participants will be advised to limit exercise in the 3 days prior to study to limit acute effects of recent exercise on insulin sensitivity.

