### 5.2 Outcome Variables

#### 5.2.1 Primary Outcome Variables

**Aim 1:** The primary efficacy outcome will be the time spent in the target range of 70-180 mg/dL during the second week on each diet. Secondary safety outcomes will include the time spent in the hypoglycemic (less than 54 mg/dL, less than 70 mg/dL) and hyperglycemic (greater than 180 mg/dL, greater than 250 mg/dL) ranges. We will also measure the average sensor glucose values, standard deviation, and coefficient of variation during the second week on each diet period. We will compare average and range of fasting beta-hydroxybutyrate levels during each diet period. Number of episodes of diabetic ketoacidosis and severe hypoglycemic events during each period (baseline, diet periods, and washout period) will also be reported.

**Aim 2:** The primary safety outcome will be the mean levels of glucagon produced in response to hypoglycemia after each diet will be measured using a 2-step hyperinsulinemic euglycemic-hypoglycemic clamp. These will be measured after 15, 30, 45, and 60 minutes of euglycemia and hypoglycemia. Secondary safety outcomes will include mean levels of other counterregulatory hormones (cortisol, epinephrine, norepinephrine), and beta-hydroxybutyrate that are produced in response to hypoglycemia during the clamp will be compared after each 2-week diet period. Fasting levels of glucagon, free fatty acids, beta-hydroxybutyrate and IGF-1 (measure of growth hormone secretion), prior to the clamp will be compared after each diet period. Secondary outcome measures will include hepatic glucose production and adipose tissue lipolysis, which will be measured using stable isotope infusions during the euglycemic and hypoglycemic portions of the clamp. We will compare differences in hepatic glucose production during each clamp between a standard and very low carbohydrate diet. Additionally, deuterated water will be utilized to differentially evaluate the contribution of gluconeogenesis and glycogenolysis to endogenous glucose production.

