**Figure 1. Schedule of visits during the study.**

#### 6.1.3 Method of Assignment/Randomization

Block randomization will be used to ensure an equal number of participants complete diets in each of the specified sequences.

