**Visit 4 (virtual/telephone or in person):**

- Anthropomorphic measures (weight, % body fat, % muscle mass, % water, % bone) – at home or on scale in office
- Insulin pumps and CGMs will be downloaded to assess glycemic control. The diabetes treatment regimen will be adjusted as clinically indicated.
  - If participants are starting the very low carbohydrate diet, insulin doses will be reduced by 10-20%, as clinically indicated, to prevent hypoglycemia.
- Second diet will be assigned.

- If participants are starting the very low carbohydrate diet, meals can be picked up 2-3 times per week at the metabolic kitchen located at Yale New Haven Hospital by study participants or by research staff. Research staff will work with participants to deliver the meals if they are unable to pick them up.
- If we are unable to acquire meals from the metabolic kitchen, we will use a mail order meal service that provides information about macronutrient content of all meals provided that meet the standards of the dietary measures.
- Participants will be instructed to check daily fasting blood ketone levels.
- Participants will receive dietary instruction and review the dietary requirements of the study. Participants will be instructed to keep a dietary record (MyFitnessPal application, written, and/or with photos) for the duration of the dietary period.
- Participants will be instructed to call the pediatric diabetes emergency line (available 24/7) in any case of severe low blood sugar, elevated ketone levels, or symptoms of ketosis. Participants will also receive education on the treatment of hypoglycemia, we will ensure that all participants have glucagon at home.
- Participants will be contacted 3 times per week (2 scheduled, 1 unscheduled) for a 24-hour dietary recall. During these telephone follow up calls, food diary will be reviewed, ketone levels reviewed, and CGM data will be uploaded and reviewed.
- Prior to the HRU/CSRU/Masonicare admission, we will recommend a standard diet be given and no food be eaten after 12am (except for in cases of hypoglycemia). A snack will be recommended at 9pm the evening prior to the clamp. Participants will be advised to limit exercise in the 3 days prior to study to limit acute effects of recent exercise on insulin sensitivity.

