## 6.5 Planned Analyses

### 6.5.1 Primary Objective Analysis

- **Statistical Analyses Aim 1:** The unadjusted between-diet-group comparison of the primary endpoint, percent time in the target range of 70-180 mg/dL during the 2nd week of each diet, will be performed using a two-sided paired t-test. The adjusted analysis will be performed using linear mixed effects (LME) modeling, with a random intercept for each subject, diet effect, and adjusting for a participant's age, BMI and duration of diabetes. The mean adjusted between diet-group difference in percent time in the target range will be reported, along with the surrounding 95% confidence intervals based on 500 bootstrapped samples (2.5th percentile and 97.5th percentile of the distribution). Secondary outcomes, including time spent with hypoglycemia (<54 mg/dL, <70 mg/dL) and hyperglycemia (>180 mg/dL, >250 mg/dL), average sensor glucose level, will be analyzed similarly to the primary outcome. The proportion of days with elevated fasting  $\beta$ -hydroxybutyrate levels ( $\geq 0.6$  mmol/L) during each diet period will be compared using paired-proportions z-test in the unadjusted analysis and using generalized linear mixed effects (GLMM) modeling (a random intercept, link=logit for the binary outcome yes/no elevated levels with Bernoulli distribution) with covariates of age, BMI, and duration of diabetes. GLMM will also be utilized in the comparison of the number of episodes of diabetic ketoacidosis and severe hypoglycemic events during each period (a random intercept, link=log for a count outcome with Poisson distribution). Statistical analyses for all aims will be implemented using R and SAS 9.4 (Cary, NC) statistical software. Statistical significance will be established at the two-sided alpha of 0.05.

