### 6.5.2 Secondary Objectives Analyses

- **Statistical Analysis Aim 2:** Appropriate mathematical transformations (e.g., natural log or square root) will be applied to each outcome of interest, as necessary, to normalize the distribution. A paired t-test will be used in the unadjusted comparison of the primary outcome, mean levels of glucagon, during each diet period. LME will be used to model the trajectories of change in mean levels of glucagon over time (baseline, 15, 30, 45, 60 minutes) during each diet period and compared between diets. We will use the Likelihood Ratio Test (LRT, a mixture of two chi-square distributions with restricted maximum likelihood – RML - estimation) to select between an LME model with just a random intercept or an LME with a random intercept and slope. The mean response will be modeled using parametric (linear and polynomial effects of time) and semi-parametric (piece-wise linear or quadratic splines) effects of time, adjusting for participants' age, BMI, and duration of diabetes. The best model will be chosen based on its fit to the data (LRT for nested models and Akaike Information Criterion, AIC, for not-nested models).

Effect sizes will be reported as the between-diet differences with bootstrapped 95% CIs. Secondary outcomes of interest will also be modeled similarly.

- **Statistical Analysis Aim 3:** Using the validated Edinburgh Hypoglycemia Symptom questionnaire, participants will be asked to verbally rate their hypoglycemia symptoms on a 7-point Likert scale (lower scores indicate fewer symptoms) during the euglycemia and hypoglycemia portions of the clamp. In the unadjusted analyses, differences between euglycemic and hypoglycemic total scores on each diet will be compared using a paired t-test. Adjusted analyses will be based on LME, similar to the analyses described in Aims 1 and 2. In the secondary analysis, we will model mean hypoglycemia awareness score by domain (e.g., autonomic, neuroglycopenic, and malaise).

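### The food instruction before the clamp differs between the two periods without a stated reason, and no planned analysis has a period term to absorb the difference

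*Combined protocol and SAP*

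**What the plan says.** Section 6.1.2 places the first clamp at Visit 3, after the first diet, and the second at Visit 5, after the second diet. The preparation for each clamp is in Section 6.3.5, under the preceding visit.

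- Visit 2 (for the first clamp): "we will recommend a standard diet be given and no food be eaten after 9pm (except for in cases of hypoglycemia". No snack is mentioned.
- Visit 4 (for the second clamp): "no food be eaten after 12am (except for in cases of hypoglycemia). A snack will be recommended at 9pm".

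The advice to limit exercise for three days is the same at both. The clamp visits are then described jointly, so nothing there explains two food rules.

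On allocation, Section 6.1.3 says: "Block randomization will be used to ensure an equal number of participants complete diets in each of the specified sequences".

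On analysis, Section 6.5.1 specifies a paired t-test and "linear mixed effects (LME) modeling, with a random intercept for each subject, diet effect", adjusted for age, BMI and diabetes duration. For Aim 2, Section 6.5.2 says "A paired t-test will be used in the unadjusted comparison of the primary outcome, mean levels of glucagon, during each diet period", followed by mixed models in time within the clamp with the same covariates. For Aim 3: "Adjusted analyses will be based on LME, similar to the analyses described in Aims 1 and 2". Section 6.5.8 lists only age, BMI and diabetes duration. None of these sections names a period, sequence or visit term.

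**The concern.** In a crossover, conditions other than the treatment should be the same in both periods, or the analysis should allow for the difference. The protocol mostly does the former: CGM alert settings, activity level and exercise before the clamp are all held constant. The last-food rule is an exception.

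Time since last food matters most for samples taken before insulin and dextrose are clamped. Section 5.2.1 names these as outcomes: "Fasting levels of glucagon, free fatty acids, beta-hydroxybutyrate and IGF-1 (measure of growth hormone secretion), prior to the clamp will be compared". Basal glucose and glycerol turnover is also measured at that stage, although Section 5.2.1 does not list it as an outcome. Glucagon during hypoglycemia (the Aim 2 primary outcome) and the Aim 3 symptom scores come later and are less exposed. Aim 1 time in range is essentially unaffected by one evening's instruction.

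At stake is some precision in secondary and exploratory comparisons. A shift between periods that is not modelled goes into the variance of the paired differences.

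**Working it through.** **1. Size of the difference in instruction.** Latest permitted intake is 9pm before the first clamp and 12am before the second, a gap of 3 h. For a 7am arrival (Section 6.3.5, Visits 3 and 5) that is 10 h against 7 h. If a participant eats up to 9pm before the first clamp and has only the 9pm snack before the second, the gap is 0 h. The range is 0 to 3 h.

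**2. How it enters the diet contrast.** Let δ be the diet effect and π the shift (second period minus first) caused by the food rule. The difference, very low carbohydrate minus standard, has mean δ − π in those who take the low carbohydrate diet first and δ + π in the others. With n_A and n_B completers in these two sequences and n = n_A + n_B, the mean difference estimates δ + π(n_B − n_A)/n. With n_A = n_B this is δ, so there is no bias.

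**3. The plan's own figure.** Section 6.4.2 uses n = 16, two-sided alpha 0.05 and a paired t-test. Noncentral t power with 15 df at effect size 0.75 is 0.8006, and n = 15 gives 0.771, so 16 is reproduced. For Aim 2, 9.5/12.5 = 0.76 gives power 0.811. Here 12.5 pg/mL is taken as the SD of the within-participant differences, as the plan's paired calculation implies.

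**4. Loss of precision at 8/8.** Without a period term the SD of the differences becomes √(12.5² + π² × 16/15). The documents give no value for π, so these shifts are assumptions. Power and type I error are simulated.

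| Assumed π, pg/mL (in SDs) | SD of differences | Paired t power | Type I error | Power with period term |
|---|---|---|---|---|
| 0 | 12.50 | 81% | 0.050 | 81% |
| 1 (0.08) | 12.54 | 81% | 0.049 | 81% |
| 2 (0.16) | 12.67 | 80% | 0.048 | 81% |
| 5 (0.40) | 13.52 | 76% | 0.036 | 81% |

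The unadjusted test becomes conservative. It does not become anti-conservative.

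**5. Cost of a period term.** It uses one degree of freedom. At 8/8 with no shift, power at effect size 0.76 is 80.7% (14 df) instead of 81.1% (15 df). The confidence interval widens by t(0.975, 14)/t(0.975, 15) = 1.006, that is 0.6%. With unequal sequences the cost rises: power with the term is about 80% at 9/7 and 78% at 10/6.

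**6. Unequal completion.** Start from 10/10 and lose 4 at random, matching the plan's 20% attrition. The number lost from one sequence is hypergeometric, so n_B − n_A takes the values 4, 2, 0, −2, −4 with probabilities 0.043, 0.248, 0.418, 0.248, 0.043. Its mean is 0 and its SD 1.835. The bias is π(n_B − n_A)/16, with mean 0 and SD 0.115π: 0.23 pg/mL at π = 2 and 0.57 pg/mL at π = 5. The most extreme split, 10/6, gives 0.5 and 1.25 pg/mL. The standard error is 12.5/√16 = 3.1 pg/mL.

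**7. Which endpoints.** Fasting samples precede the clamp phases. Hypoglycemia follows 150 + 90 + 120 = 360 min of them, with insulin available to hold basal glucose at about 90–110 mg/dL.

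**The case against.** The strongest reply is that little is at stake. Both rules give an overnight fast, the instruction is only a recommendation, both versions exempt treatment of hypoglycemia, and real intake may end near 9pm on both evenings. The mismatch may simply be one visit section updated and the other not. The figures above are for glucagon during hypoglycemia, the less exposed endpoint, and the visible loss needs a 5 pg/mL shift, more than half the 9.5 pg/mL target effect. All of this stands, and it is why the point is minor. It does not remove the inconsistency: staff following the text would prepare participants differently for the two clamps.

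It is also fair to say that a missing period term is a general crossover question. That is so, but here the protocol itself creates a known difference between periods.

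A second objection is that a new rule cannot undo the past. Section 5.3 refers to patients who have already completed the study, so some participants may have had both clamps. This limits the wording change, but not the period term.

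Two stronger readings are tempting. A reader might infer that the food rule biases the diet comparison. The documents do not support that: the rule is tied to the visit, blocking aims at equal sequences, and nothing suggests dropout related to sequence. A reader might also infer that the standard diet recommended before each clamp is the comparator diet, so that the contrast is diluted on the eve of measurement. The term is undefined, and Section 6.4.2 uses it for the comparator, but the rest of the text points the other way. Section 6.1.2 has participants follow each diet for 2 weeks and then attend the clamp, and Section 5.2.1 describes hormone levels "produced in response to hypoglycemia during the clamp will be compared after each 2-week diet period".

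**Conclusion.** The point holds and is minor. That the two instructions differ, and that no period term is planned, is plain from the text. The consequence is less certain. With balanced sequences the diet estimate is unbiased. If completers are lost regardless of sequence, the expected bias is zero and its spread is small against the standard error. What remains is some added variance in the fasting comparisons, and less in the hypoglycemic ones.

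The power figures rest on assumed shifts and on 12.5 pg/mL as the SD of differences. They carry over to another endpoint only if its effect size is also 0.76, and the documents give no effect size for the fasting measures. They show that a modest shift costs about one point of power or less and that a large one would cost about five. They do not show that either occurs. The meaning of standard diet before the clamp is a matter for the investigators to clarify, not a demonstrated flaw.

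**What to change.** 1. Use one last-food and snack rule for both clamps, chosen by the investigators, for participants who have not yet had their first clamp. For anyone between clamps, repeat the rule used at the first clamp where possible, so that each participant's two clamps are prepared alike.
2. Add period as a fixed effect in the Aim 2 and 3 mixed models. This also covers participants already studied under the two rules. If the rule changes partway, a single term absorbs the average shift, which is adequate for an effect of this likely size.
3. In the same amendment, ask the investigators to state what standard diet means before the clamp. The answer is theirs to give.

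The cost is one wording amendment through the IRB, with no added visit or procedure, and one degree of freedom. At 8/8 with no shift that means power of 80.7% instead of 81.1% and a confidence interval 0.6% wider. The cost is somewhat more if the sequences end up unequal.
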